8.1.1.1 Pre-prophylaxis treatment

Pre-prophylaxis is optional and is the period before start of regular prophylaxis.

During pre-prophylaxis the following dosing regimen applies:

- approximately 60 U/Kg N8-GP within the range of 50-75 U/Kg bw, see Section 5.3
- individualised prophylactic dosing intervals but less frequent than every 7th day(once weekly)
- on-demand treatment of bleeding episodes

See further Section 5.3.1.

Dosing visits during the pre-prophylaxis period can be performed at any time until ED 20 being either part of visits in Table 2-1 or being registered as an unscheduled visit if the dose is not part of Table 2-1. Visits during the pre-prophylaxis period without dosing should be performed as unscheduled visits, see Section 8.1.9.

The site must make sure that the patient's parent(s)/LAR(s) are contacted at least at least every 12 weeks \pm 1week if no planned visits, Section 8.8.4.

Visits 1-6 are when the patient needs treatment of a bleeding episode and/or planned individually per patient at the investigator and patient's parent(s)/LAR(s) discretion.

8.1.1.2 Prophylaxis treatment

A patient may change from pre-prophylaxis to prophylaxis at any time during the pre-prophylaxis period or must be initiated when the patient has reached 20 EDs, or has turned 24 months of age, whatever comes first.

Protocol v 1 | 44 of 114

Protocol		Date:	04 November 2013	Novo Nordisk
Trial ID: NN7088-3908	CONFIDENTIAL	Version:	1.0	
UTN: U1111-1148-1897	CONFIDENTIAL	Status:	Final	
EudraCT No.: 2013-004025-88		Page:	45 of 114	

The dosing frequency during main phase is individualised within the following interval: twice weekly, every 3rd day or every 7th day. Changes to the regimen should be recorded in the IV/WRS. If changes occur between visits, it should be recorded in an unscheduled visit, see Section 8.1.9.

For patients that enter the prophylaxis treatment after a period of pre-prophylaxis the next visit in the sequence will be determined by the numbers of EDs.

8.1.1.3 Wash-out prior to visits

A washout period is required prior to visits including inhibitor testing. The required wash-out period is at least 72 hours.

In case the wash-out period has not been fulfilled the scheduled visit should be re-scheduled unless the visit is due to a bleeding episode treated at site during the pre-prophylaxis period or prior to initiating home treatment.

8.1.2 Visit 1 – first dosing with N8-GP

V1 will take place after the screening visit (V0) whenever the first treatment of N8-GP is administered, if not already combined with V0.

In case of subjective signs of illness and/or fever within 48 hours prior to the first injection of N8-GP the dose should be postponed, if possible.

The patient will continue treatment on either:

- **Pre-prophylaxis treatment**. See Sections 5.3.1 and 8.1.1.1.
- Prophylaxis treatment. See Sections 5.3.1 and 8.1.1.2.

Assessments for V1 are listed in Table 2–1. In case V0 and V1 have been combined into one visit, assessments should only be performed once.

Reminders

- Next visit should be scheduled if applicable, see Sections 8.1.1.1 and 8.1.1.2.
- In case V2 is not planned or performed within 3 month from visit 1 the Investigator must contact the patient's parent(s)/LAR(s) at least every 12 weeks \pm 1week. See Sections 8.8.4 and 8.1.9
- Drug accountability of trial product at V1 must be recorded in the IV/WRS, see Section 10
- Recording of body weight, see Section 8.3.1, and dispensing of N8-GP for trial site dosing via IV/WRS, see Section 10.

8.1.3 Visit 2, 3, 4-6 – main phase

The 2 first N8-GP injections must take place at trial site (V1+V2). Hereafter the injections can be administered at the trial site or outside the trial site.

Protocol v 1 | 45 of 114

Protocol		Date:	04 November 2013	Novo Nordisk
Trial ID: NN7088-3908	CONFIDENTIAL	Version:	1.0	
UTN: U1111-1148-1897	CONFIDENTIAL	Status:	Final	
EudraCT No.: 2013-004025-88		Page:	46 of 114	

If the treatment is given at site the doses should be registered in the eCRF. If not given at site, the dose should be registered in the eDiary.

Visits at ED: 2, 5 ± 1 ED, 10 ± 2 EDs, 15 ± 2 EDs, 20 ± 2 EDs.

The visits should be scheduled taking into account the patient's regular dosing day(s) in the week.

Assessments for V2-V6 are listed in Table 2-1.

Reminders

- In case next visit is not planned or performed within 3 month from the previous visit the investigator must contact the patient's parent(s)/LAR(s) at least every 12 weeks ± 1week. See Sections 8.8.4 and 8.1.9
- All visits must be planned to allow for the required wash-out of 72 hours, see Section 8.8.3.1
- Recording of body weight, see Section 8.3.1, and dispensing of N8-GP for trial site dosing and home treatment from visit 2 must be performed via IV/WRS, see Section 10
- Drug accountability of trial product must be recorded in the IV/WRS, see Section 10
- Investigator must ensure that patient's parent(s)/LAR(s) return any trial medication that would expire during the next home treatment period
- eDiary dispensing at V2 or when treatment outside trial site is initiated, see Section 8.8.3.1
- eDiary training, see Section 8.8.3

8.1.4 **Visit 7-8 – main phase**

From V6 all patients (including patients previously on pre-prophylaxis) will be on prophylaxis treatment with N8-GP on twice weekly, every 3rd day or every 7th day. Between the visits the patient will receive N8-GP treatment at home if comfortable with home administrations or at the site, see Section 8.1.12.

Visits at EDs: 30 ± 2 EDs, and 40 ± 2 EDs.

The visit should be scheduled taking into account the patient's dosing day.

Assessments for V7-V8 are listed in Table 2–1.

Reminders

- An appointment for the next visit should be made
- All visits must be planned to allow for the required wash-out of 72 hours, see Section 8.8.3.1
- Recording of body weight, see Section 8.3.1, and dispensing of N8-GP for trial site dosing/home treatment must be performed via IV/WRS, see Section 10
- Drug accountability of trial product must be recorded in the IV/WRS, see Section 10

Protocol v 1 | 46 of 114

- Home treatment training, if the trial site suspects that the patient's parent(s)/LAR(s) is not fully confident with administration and how to deal with safety related signs and symptoms, see Sections 8.5 and 8.6
- eDiary training, see Section 8.8.3
- eDiary compliance review, see Section 12.3.

8.1.5 Visit 9 – end of main phase

Visit 9 should take place at either ED 50, ED 51 or ED 52.

Assessments for V9 are listed in Table 2–1.

Reminders

- An appointment for the next visit should be made
- Next visits must be planned to allow for the required wash-out of 72 hours, see Section 8.8.3.1
- Recording of body weight, see Section 8.3.1, and dispensing of N8-GP for trial site dosing/home treatment must be performed via IV/WRS, see Section 10
- Drug accountability of trial product must be recorded in the IV/WRS, see Section 10
- Home treatment, if the trial site suspects that the patient's parent(s)/LAR(s) is not fully confident with administration and how to deal with safety related signs and symptoms, see Sections 8.5 and 8.6
- eDiary training, see Section 8.8.3 and 12.3
- eDiary compliance review, see Section 12.3

8.1.6 Visit 10-13 – extension phase

The patient will continue prophylaxis throughout the extension phase, with 60 U/Kg in the regimen of every 3rd day, twice weekly, every 4th day, every 5th day, every 6th day or every 7th day. See Table 5–1. Changes to the regimen should be recorded in the eCRF. If changes occur between visits, it should be recorded in an unscheduled visit, see Section 8.1.9.

Visit at EDs: 60 ± 2 EDs, 70 ± 2 EDs, 80 ± 2 EDs, and 90 ± 2 EDs.

The visits should be scheduled taking into account the patient's dosing day.

The duration of the extension phase is between 6 months and 1 year depending on the dosing frequency, for a patient to achieve a total of 100 EDs.

Assessments for V10-V13 are listed in Table 2–1.

Reminders

• An appointment for the next visit should be made

Protocol v 1 | 47 of 114

- Next visits must be planned to allow for the required wash-out of 72 hours, see Section 8.8.3.1
- Recording of body weight, see Section 8.3.1, and dispensing of N8-GP for trial site dosing/home treatment must be performed via IV/WRS, see Section 10
- Drug accountability of trial product must be recorded in the IV/WRS, see Section 10
- Home treatment, see Sections 8.1.12 and 8.8.2.
- eDiary training, see Section 8.8.3
- eDiary compliance review, see Section 12.3

8.1.7 Visit 14 - end of extension phase

Visit 14 should take place at either ED 100, ED 101 or at ED 102.

Assessments for V14 are listed in Table 2–1.

Reminders

- An appointment for the next visit should be made
- Next visit must be planned to allow for the required wash-out of 72 hours, see Section 8.8.3.1
- Recording of body weight, see Section 8.3.1, and dispensing of N8-GP for trial site dosing/home treatment must be performed via IV/WRS, see Section 10
- Drug accountability of trial product must be recorded in the IV/WRS, see Section 10
- eDiary compliance review, see Section 12.3

8.1.8 Visit 15-X until end of trial

If N8-GP is not commercially available in a patient's country at the time of visit 14, the trial period may be extended with visits that are scheduled 24 weeks \pm 4 weeks. These additional visits are referred to as visit 15 to visit X, where X can be any visit from 16 and onwards. This option for the patient to continue in the extension phase of the trial may be offered until either N8-GP becomes commercially available in the relevant country, or until the marketing authorisation application is rejected in the relevant country unless the N8-GP trial, part of the trial or a trial site is terminated by Novo Nordisk or a relevant authority for any reason, the End of Trial visit must be scheduled within 1 month provided always that the Last Patient Last Visit for the prophylaxis period until end of trial will be no later than 13 May 2019 whether or not the product is commercially available in the relevant country at this time.

At every dosing visit from V15-VX, drug will be dispensed to cover up to 3 months of treatment. Depending on patient's treatment regimen, additional dispensing visits might need to be scheduled to cover treatment in the period between visits.

Protocol v 1 | 48 of 114

Page:

49 of 114

Assessments for V15-VX are listed in Table 2–1.

8.1.9 End of trial visit

EudraCT No.: 2013-004025-88

The EOT visit can take place at any time after completion of 100EDs or if the patient is withdrawn from the trial.

Assessments for the EOT are listed in Table 2–1

Reminders

- Drug accountability of trial product must be recorded in the IV/WRS, see Section 10
- eDiary compliance review, see Section 12.3
- eDiary LogPad collection, see Section 8.8.3.1
- Complete EOT form

8.1.10 Unscheduled visit

Unscheduled visits of trial related character can be performed at any time during the trial and the purpose must be documented.

The following forms can be found in the unscheduled visit in the eCRF:

- Central lab
- Bleeding episodes
- Dosing of N8-GP
- Surgery
- PK session
- Change of regimen

8.1.11 ITI Visit

N8-GP treatment may continue in case of low titre FVIII inhibitor (\leq 5BU) confirmed by central laboratory, that does not result in clinically ineffective treatment with N8-GP. Patients may follow the visit flow either as described in Table 2–1, or visits at the discretion of the investigator.

In case of high titre FVIII inhibitor (>5BU) confirmed by central laboratory the investigator must decide how to proceed with treatment. Novo Nordisk will communicate when ITI is allowed in this trial, see Section 5.3.6.

If ITI is initiated, the patient will follow a visit schedule prescribed by the investigator and according to local standard of practice. Monthly visits are recommended, and the below listed assessments are recommended to be performed:

Protocol v 1 | 49 of 114

Page:

50 of 114

Adverse Events

EudraCT No.: 2013-004025-88

- Concomitant medication
- Sampling for inhibitor test
- Sampling for FVIII activity test
- Bleeding episode evaluation
- Review of eDiary
- Body measurements, see Section 8.3.1

Treatment of bleeding episodes with bypassing agents is allowed at the discretion of the investigator according to local practice, see Section 11.2.

Reminder

• Follow up on any AEs according to Section 11.2

For patients returning to regular prophylaxis N8-GP treatment, the visit schedule is taken up from V9 end of main phase Table 2–1, even when the corresponding total ED does not match.

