5.3.6 Treatment of patients with FVIII inhibitors

Approximately 20–30% of PUPs with severe haemophilia A develop inhibitors to infused FVIII rendering use of such replacement therapy ineffective. Patients who develop inhibitory antibodies remain at higher risk for morbidity and mortality associated with recurrent or uncontrolled bleeding events.

The majority of haemophilia patients with inhibitors develop high-titre (> 5 BU) inhibitors, and demonstrate an anamnestic rise in their inhibitor titre when re-exposed to FVIII. In these patients even frequent, high-dose FVIII substitution therapy becomes ineffective in controlling bleeding episodes as the infused coagulation factor products are neutralised by the inhibitor. Administration of FVIII bypassing agents (rFVII or activated prothrombin complex concentrates) becomes necessary for treatment of bleeding episodes.

Treatment of bleeding episodes with by-passing agents, i.e. rFVIIa or APCC according to local standard care, is allowed for patients who develop FVIII inhibitors within this trial. By-passing agents are not considered trial medication.

The ultimate goal of treatment in patients with high-titre inhibitors is to permanently eradicate the inhibitor by immune tolerance induction therapy (ITI), thereby making it possible for the patient to be treated routinely with FVIII replacement therapy. The therapeutic concept is based on long-term uninterrupted high exposure to FVIII in an effort to sufficiently tolerize the immune system. In that state, the clinical responsiveness to FVIII replacement therapy is restored.

Based on the available evidence, all patients with high-titre inhibitors (> 5 BU) should undergo ITI using the same type of product that the patient was using at the time of inhibitor development. This approach is supported by an international expert panel which concurred with treatment guidelines which recommend that ITI should be conducted with the same concentrate as the one against which antibodies were developed. This should ensure successful tolerance induction and reduce the risk of further inhibitor development to new molecules. It may therefore be expected that N8-GP will be favourable over the use of commercially available FVIII products for ITI in patients who developed FVIII inhibitors within this trial.

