16.4.2.3 Incidence of high titre inhibitors

The rate of high titre inhibitors (defined as inhibitor titre > 5BU) will be reported similar to the primary endpoint

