5.3.6 Treatment of patients with FVIII inhibitors

Patients who develop FVIII inhibitors during this trial may receive N8-GP and/or Treatment of bleeding episodes with by-passing agents, e.g. i.e. rFVIIa or APCC for treatment of bleeding episodes according to local standard care is allowed for patients who develop FVIII inhibitors within this trial. However, N8-GP dose levels used should not exceed 75 U/kg as a single dose and not exceed 200 U/kg as a maximum 24 hour dose. Treatment with FVIII concentrates other than N8-GP is not allowed. By-passing agents are not considered trial medication.

The ultimate goal of treatment in patients with high-titre inhibitors is to permanently eradicate the inhibitor by immune tolerance induction therapy (ITI), thereby making it possible for the patient to be treated routinely with FVIII replacement therapy again. The therapeutic concept is based on long-term uninterrupted high exposure to FVIII in an effort to sufficiently tolerise the immune system. In that state, the clinical responsiveness to FVIII replacement therapy is restored.

Novo Nordisk plans that Patients who develop inhibitors, within this trial, will be offered continued treatment with N8-GP, including ITI for a maximum of 24 months. ITI with N8-GP will not be initiated until Novo Nordisk has reviewed the clinical data available after completion of the N8-GP pivotal and surgery trial (pathfinderTM2 and pathfinderTM3), and of the paediatric PTP trial (pathfinderTM5) data needed for opening the paediatric PUP trial according to EMA requirements.

It is expected to use a N8-GP dosing regimen for ITI similar to local standard care/guidelines applied for ITI with marketed FVIII products. For each individual patient, ITI regimens with N8-GP would have to be reviewed by the investigator every month, and more formally reviewed every 3 months by Novo Nordisk.

If patients with (usually low titre) inhibitors respond well to treatment with N8-GP then the patient can continue the prophylaxis. These patients can still start ITI treatment within 6 months after the

Protocol Amendment
Trial ID: NN7088-3908

CONFIDENTIAL

Date: 20 March 2015 | Novo Nordisk
Version: 2.0

UTN: U1111-1148-1897 CONFIDENTIAL Status: Final Page: 14 of 41

confirmatory inhibitor test. If the inhibitor is still present (BU>/=0.6) at 6 months after the confirmatory test the patient must start ITI or withdraw from the trial.

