6.4 Withdrawal criteria

The patient must be withdrawn if the following applies:

- 1. Dosed in the trial, but not fulfilling the inclusion and/or exclusion criteria
- 2. Anaphylactic reaction to the trial product, for definition see Section 11.1

Major surgery before 50 EDs, see Section 5.3.4

Significant thromboembolic event, see Section 11.1

Incapacity or unwillingness to follow trial procedures

Use of coagulations factors other than N8-GP or anti-coagulants unless in relation to ITI

ITI treatment has not been started within 6 months from the date of confirmation of positive FVIII inhibitor (BU $\geq 0.6 \frac{\text{ml}}{\text{ml}}$) unless the FVIII inhibitor has disappeared (BU<0.6) under continuous prophylactic treatment within the 6 months.

FVIII inhibitor titre decline from peak level is less than 20% after 12 months of ITI treatment FVIII inhibitor is positive (BU $\geq 0.6 \frac{\text{ml}}{\text{ml}}$) after 24 months of ITI treatment.

After completed ITI treatment (maximum 24 months), prophylaxis treatment as described in the protocol is not resumed/started

Positive inhibitor test result from visit 1 before first dosing (a positive sample does not have to be confirmed in a confirmatory test)

Participation in another clinical trial throughout the trial.

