4.2.2 Secondary Endpoint

Frequency of Adverse events (AEs) including serious AEs and Medical Events of Special Interest (MESI).*

Incidence of confirmed high titre inhibitors (defined as inhibitor titre > 5BU)*

Number of breakthrough bleeding episodes during prophylaxis with N8-GP (annualised bleeding rate).*

Haemostatic effect of N8-GP in treatment of bleeding episodes, assessed by a predefined 4-point haemostatic response scale ("excellent", "good", "moderate" and "none").*

Consumption of N8-GP for prophylaxis (number of injections and U/Kg per month and per year)

Consumption of N8-GP for treatment of bleeding episodes (number of injections and U/Kg required per bleeding episode)

Total consumption of N8-GP per patient (prevention and treatment of bleeding episodes) per month and annualised value

Outcome of ITI, assessed by a predefined 4-point ITI outcome scale ("success", "partial success", "failure", "other")

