- Any new text is written in italics.
- Any text deleted from the protocol is written using strike through.

Protocol Amendment no 8		Date:	15 June 2020	Novo Nordisk
Trial ID: NN7088-3908	CONFIDENTIAL	Version:	1	
UTN: U1111-1148-1897	CONFIDENTIAL	Status:	Final	
EudraCT no.: 2013-004025-88		Page:	4 of 10	

2 Changes

Following sections in the protocol are affected by this eighth protocol amendment:

1 Summary

[...]

Time frames for evaluation of Objectives/Endpoints

All objectives/endpoints will be evaluated when the first 50 PUPs have reached at least 50 exposure days with V9 dates, when the first 100 PUP have reached 100 exposure dates, and at end of trial. End of trial will be up to 4 years after the *first* patient has reached 100 exposure dates days.

[...]

Trial design:

[...]

The European medical agency requires required submission of safety and efficacy data from minimum 50 exposure days in at least 50 patients for approval of the indication in PUPs, with a post-approval commitment to follow- at least 100 patients for a minimum of 100 exposure days. When the first 50 patients have reached a minimum of 50 exposure days and V9, the analysis and evaluation for the main trial report will be performed. All patients Patients may continue in the extension phase for the purpose of collecting data for a minimum of 100 exposure days in at least 100 patients.

Protocol Amendment no 8
Trial ID: NN7088-3908
Version: 1
CONFIDENTIAL
CONFIDENTIAL
Version: 1
CONFIDENTIAL

UTN: U1111-1148-1897 EudraCT no.: 2013-004025-88 Version: 1
Status: Final
Page: 5 of 10

2 Flow chart

Table 2-1 Flow chart visits and assessments

Visit number	0 ¹	11	2	3	4-6	7-8	9	10-13	14	15-X ¹⁹	EOT
Visit purpose	Screening	Dosing	Dosing	Dosing	Dosing	Dosing	End of main	Dosing	End of extension	Dosing (until EOT)	End of Trial
Time of visit (ED(s)) ²	0	1	2	5	10, 15, 20 3	30,40	50	60, 70, 80, 90	100	NA	
Visit interval (ED(s)) ²		0	0	±1	±2	±2	+2	±2	+2	24w±4w	
CENTRAL LABORATORY ASSESSMENTS											
FVIII activity – trough9	X ⁸	Х		Х	Х	Х	Х	Х	Х	Х	Х
FVIII activity – recovery (30 min post-dose)		Х		Х	х	Х	Х	х	х	х	
N8-GP/FVIII binding antibodies ⁹		х		х	х	х	х	х	х	х	х
PEG antibodies9		Х		X	X	X	Х	X	Х		Х
FVIII inhibitor test ⁹		X ¹⁸		Х	Х	Х	Х	Х	Х	Х	Х
HIV antibodies	(X) ¹⁰										
CD4+ lymphocyte count and HIV viral load	(X) ¹⁰										
Haematology	Х	X ¹¹					Х		Х		Х
Biochemistry	Х	X ¹¹					Х		Х		Х
F8 + HLA genotype testing	(X) ¹²	(X) ¹²									

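### Section 8.1.11 sets no minimum inhibitor-test interval for low-titre patients on discretionary visits, so a silent or transient rise above 5 BU may be missed

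*Combined protocol and SAP*

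**What the plan says.** Section 8.1.11 of the protocol covers a patient with a centrally confirmed low-titre inhibitor "that does not result in clinically ineffective treatment with N8-GP". Treatment may continue, and the patient may follow Table 2-1 "or visits at the discretion of the investigator". No test interval is attached to the second route. The Amendment 2 extract of 8.1.11 does not change this sentence, and neither does any later amendment extract.

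The "FVIII inhibitor test" row of Table 2-1 is where the scheduled central tests sit: V1, V3, V4-6, V7-8, V9, V10-13, V14, V15-X and EOT.

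Section 5.3.6 as changed by Amendment 2 adds: "If patients with (usually low titre) inhibitors respond well to treatment with N8-GP then the patient can continue the prophylaxis". If the inhibitor is still present 6 months after the confirmatory test, the patient must start ITI or leave the trial. Section 6.4 makes an exception if the inhibitor has disappeared by then.

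The endpoint concerned is listed and starred in section 4.2.2: "Incidence of confirmed high titre inhibitors (defined as inhibitor titre > 5BU". Section 16.4.2.3 says "The rate of high titre inhibitors (defined as inhibitor titre > 5BU) will be reported similar to the" primary endpoint, that is, as a rate with an exact binomial one-sided 97.5% upper limit (section 16.3).

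**The concern.** A patient first confirmed at low titre enters the high-titre numerator only if a later sample exceeds 5 BU and is confirmed. Section 5.3.6 says that most inhibitor patients reach high titre and "demonstrate an anamnestic rise in their inhibitor titre when re-exposed to FVIII". The patients covered by 8.1.11 continue to be exposed, yet they are the group for whom the plan makes scheduled sampling optional.

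Two things are at stake.

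- **The endpoint.** A missed conversion stays in the denominator and leaves the numerator, so the error can only lower the rate and its upper limit. How often samples are taken would also depend on the investigator, so ascertainment may differ by site.
- **The peak titre.** Withdrawal criterion 8 in section 6.4 reads "FVIII inhibitor titre decline from peak level is less than 20% after 12 months of ITI treatment", and the ITI failure category added by Amendment 3 uses the same 20% threshold. Sparse sampling may under-measure the peak.

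**Working it through.** The plan gives no figure for test frequency on the discretionary route or for missed conversions, so there is none to reproduce.

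**1. Scheduled tests that can lapse.** Inputs: Table 2-1 tests at ED 5, 10, 15, 20 and then every 10 EDs to ED 100; the 6-month limit in 5.3.6, taken as 26 weeks; the three main-phase dosing frequencies in Table 5-1. EDs in the window = 26 weeks × EDs per week.

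| Inhibitor found | Dosing | EDs in 26 weeks | Reaches ED | Scheduled tests | Count |
|---|---|---|---|---|---|
| ED 20 | twice weekly | 26 × 2 = 52 | 72 | 30, 40, 50, 60, 70 | 5 |
| ED 20 | every 3rd day | 26 × 7/3 = 60.7 | 80.7 | 30, 40, 50, 60, 70, 80 | 6 |
| ED 20 | once weekly | 26 × 1 = 26 | 46 | 30, 40 | 2 |
| ED 10 | twice weekly | 52 | 62 | 15, 20, 30, 40, 50, 60 | 6 |
| ED 10 | every 3rd day | 60.7 | 70.7 | 15, 20, 30, 40, 50, 60, 70 | 7 |
| ED 10 | once weekly | 26 | 36 | 15, 20, 30 | 3 |

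Table 5-1 allows dosing as needed for low-titre patients, so these counts are approximate. After ED 100 the scheduled visits are 24 ± 4 weeks apart, so only about one test (26/24 = 1.1) is at stake there.

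**2. What remains fixed on the discretionary route.** The 6-month rule requires inhibitor status to be known once. Showing disappearance takes two tests a month apart plus recovery of at least 66% of expected (8.4.2.2). A patient who stays positive could reach month 6 on a single further sample.

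**3. Effect on the endpoint, for illustration.** Inputs: about 30% inhibitors (section 3.1.1); a high-titre share of 60%, assumed because 5.3.6 says only that it is the majority; 50 evaluable patients, assumed. True cases = 50 × 0.30 × 0.60 = 9. Upper limit for x cases in n patients = 0.975 quantile of Beta(x + 1, n − x).

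| n | True cases | Missed | Rate | Upper limit |
|---|---|---|---|---|
| 50 | 9 | 0 | 9/50 = 18.0% | 31.4% |
| 50 | 9 | 1 | 8/50 = 16.0% | 29.1% |
| 50 | 9 | 2 | 7/50 = 14.0% | 26.7% |
| 100 | 18 | 0 | 18/100 = 18.0% | 26.9% |
| 100 | 18 | 2 | 16/100 = 16.0% | 24.7% |
| 100 | 18 | 4 | 14/100 = 14.0% | 22.4% |

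Each missed case costs 1/n: 2.0 points at 50 patients, 1.0 point at 100. Shares of 50% and 70% give 8 and 10 true cases at n = 50 after rounding. One missed case then moves 16.0% (29.1%) to 14.0% (26.7%), or 20.0% (33.7%) to 18.0% (31.4%).

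**4. Effect on the peak.** Decline = 1 − (titre at 12 months ÷ peak). A peak recorded too low makes the decline look smaller, so a patient could fall under the 20% threshold because of sparse sampling. This error does not flatter the product.

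**The case against.** The strongest reply is that the plan has other ways of finding a rise.

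- Suspicion of an inhibitor from more bleeds, difficult bleeds, low recovery or trough, or a positive local test requires an unscheduled visit and a central sample (8.4.2.2). Any local inhibitor test needs a central duplicate.
- Section 5.3.6 says that FVIII stops controlling bleeds at high titre, so a sustained rise should show clinically. The discretionary route also applies only while treatment works.
- Surgery requires a central sample unless one was sent within 30 days (8.7, Amendment 2). A withdrawn patient should have an EOT visit, which includes the test.
- Section 3.3 promises close follow-up, a confirmed inhibitor is an SAE that is followed up, and families are contacted every 12 weeks if visits are more than 3 months apart.
- Discretion may also mean more testing, and the endpoint is descriptive (16.4.1).

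Most of this stands, and it confines the exposure to silent, transient or unconfirmed rises over about 6 months. It does not close the gap. Scheduled trough and recovery samples are themselves Table 2-1 items, so dropping those visits weakens one of the triggers. The 12-week contact may be a telephone call. Surgery may not occur, and the EOT test comes only on leaving.

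A reader might infer that inhibitor testing stops once a low titre is confirmed. The documents do not support that: 8.1.11 permits the discretionary route but does not impose it, and Table 2-1 remains an option. A reader might also infer that inhibitor-free patients are always tested every 5 to 10 EDs. That is untrue after ED 100.

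**Conclusion.** The point holds as a cheap improvement to a stated rule. Section 8.1.11 leaves a window of up to about 6 months after confirmation with no required scheduled central inhibitor test, putting about 2 to 6 scheduled tests at stake from ED 20, depending on dosing frequency. The high-titre endpoint may be under-ascertained, and any such error lowers the reported rate and its limit.

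It would go too far to say that the endpoint is under-ascertained. The documents do not show how many patients would use the discretionary route, how often they would be sampled, or how many would rise and fall unseen. The 2.0-point shift per missed case rests on an assumed 50 evaluable patients.

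On the peak titre, a reader might infer that only values before ITI count. Sections 5.3.6.1 and 6.4 refer to a peak without that limit, so samples taken during ITI may contribute, and the claim is only that the peak may be under-measured.

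**What to change.** Add to 8.1.11 that patients with a confirmed low-titre inhibitor who continue N8-GP outside ITI have the central FVIII inhibitor sample at least at the Table 2-1 time points, whichever visit flow is used, with all other assessments still at the investigator's discretion.

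This takes one sentence in an amendment and changes no dose or treatment rule. The samples are already planned in Table 2-1, and Amendment 2 accepts antibody samples within ±1 week of a visit (EOT: up to 1 week before only). The cost is some loss of visit flexibility and the need to stay within the blood-volume limit of section 8.4.3. After ED 100 the sentence adds little, because Table 2-1 itself has a test only about every 24 weeks there. No change to sampling during ITI is proposed: section 16 treats patients starting ITI like withdrawals and their ITI data as exploratory, so it would not serve this endpoint.
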